### 11.0 Sample Size

The AMBU® AURAGAIN™ and TELEFLEX® LMA PROTECTOR™ are FDA approved SGADs that can be used for ventilation, and as a conduit for intubation. For patients in the general hospital setting, each device has exhibited a relatively high success rate of at least 90% as a ventilatory device. Success is defined as the insertion and placement of a SGAD on the first attempt. Success rates will be computed as proportions for each study arm. Taking the ratio of the success rates for each study arm will derive the relative risk. A two-sided 95% confidence interval will have the following lower and upper limits: (0.945, 1.255) assuming a relative risk of 1.089 (ie. success rate for study arm 1 = 0.90 and success rate for study arm 2 = 0.98) and 25 patients in each treatment arm.

### 12.0 Ethics

#### Institutional Review Board (IRB)

Prior to participating in this investigation, the site will be required to obtain approval from its governing IRB. The Principal Investigator is responsible for obtaining and maintaining IRB approval to participate in this investigation. Prior to subject enrollment, a signed copy of the IRB approval letter addressed to the Investigator certifying study approval must be submitted to the Sponsor. The IRB for this study is the local IRB at the University of Texas MD Anderson Cancer Center in Houston, TX (IRB00000308, IRB00003763, IRB00004604 or IRB00008445).

The Investigator will report to the Sponsor immediately if, for any reason, the approval to conduct the investigation is withdrawn. This report will include a complete description of the reason(s) for which approval was withdrawn.

#### Subject Data Confidentiality

All information recorded on the anesthetic records will be kept strictly confidential and all data will be kept in a data logbook locked in the office of the principal investigator. We will record patients only by study code number.

Information about study subjects will be kept confidential and managed according to the requirements of the Health Insurance Portability and Accountability Act of 1996 (HIPAA). Patient data will be entered into a password protected electronic spreadsheet and online database (i.e. REDCap). Only the investigators, who have been invited to participate in the study and who are registered with the IRB, as well as have documented completion of all IRB and HIPAA regulations will have access to the file and password. No identifiable data will be collected. Electronic records will be stored for five years after study conclusion on the agreed upon investigator's laptop computer, after which time they will be deleted. If there is a breach in confidentiality or violation of IRB and HIPAA regulations, the IRB will be notified in a timely manner (within 7 days) and appropriate actions taken thereafter.

Sponsor will consider all information and data sent to Sponsor concerning a subject or their participation in this investigation as confidential. Only authorized Sponsor personnel will have access to these confidential files and have the right to inspect and copy all of the records pertinent to this study for data verification. This may include medical information gathered prior to the onset of the study. All data used in the analysis and reporting of this investigation will be conducted without identifiable reference to specific subject name. The site will maintain a list matching each subject's name with the study identification.

Data collected and stored by Sponsor will be free of identifying information such as subject name and medical record numbers. Any photos taken during the study will make every effort not to include subject faces or other identifying marks such as scars or tattoos.

In order to ensure compliance with the Health Insurance Portability and Accountability Act (HIPAA), all subjects enrolled in the study will be required to provide authorization to disclose Protected Health Information (PHI). This authorization will be included in the informed consent document as required by the IRB. In all study reports and in any resulting publications, subjects will not be referred to by their initials and/or study identification number.

### 13.0 Reporting Requirements

#### Adverse Events

For study conduct purposes, adverse events will be categorized at the investigative site into two groups: Serious Adverse Events, and Non-Serious Adverse Events. The Investigator as either related to the device or its deployment, or not related to the device or its deployment will assess the causal relationship of each adverse event. Each Adverse Event assessed as being related to the device or its deployment will also be assessed by the Investigator as being anticipated or unanticipated.

#### Adverse Events Definitions

Adverse Event (AE): An Adverse Event is any undesirable clinical event occurring to the subject during clinical study, whether or not it is considered related to the investigational product. This includes a change in a subject's condition or laboratory results, which has or could have a deleterious effect on the subject's health or well-being. An Adverse Event that is related to the investigational device may be referred to as an Adverse Device Effect (ADE).

An adverse event does not include:

- Medical or surgical procedures; the condition that leads to the procedure is not an adverse event
- Pre-existing disease, conditions, or laboratory abnormalities present at the start of the study that do not worsen in frequency or intensity
- Situations where an untoward medical occurrence has not occurred (e.g., hospitalizations for cosmetic or elective surgery or social/convenience admissions)
- Expected post-operative course

Unanticipated Adverse Device Effect (UADE): Any device related adverse event, the nature or severity of which is not consistent with or listed in the applicable product information (e.g., instructions for use, subject informed consent document, subject information brochure [if applicable], promotional literature) or any other unanticipated serious problem associated with a device that relates to the rights, safety, or welfare of subjects.

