### **2.0 Objectives and Hypothesis**

The purpose of this study is to estimate the ratio or difference in success rate of both the Ambu® AuraGain™ and Teleflex® LMA Protector™ during insertion and placement into an airway. Other findings include ease of supraglottic airway device (SGAD) insertion, anatomical fit of the SGAD (i.e. SGAD displacement, bloodstaining), rate of successful ventilation and intubation, functionality of gastric drainage channel (via orogastric tube insertion through each SGAD; to ensure easy insertion), oropharyngeal leak pressure (OLP; measured by a portable, handheld manometer), and postoperative complications in elective surgical patients who are not expected to have a difficult airway. Also, a fiberoptic assessment (with the Ambu® aScope™ 3 Slim) of the glottic view via the SGAD device and signs of airway morbidity will be investigated.

**2.1 Primary:** The ratio or difference in success rates of either the Ambu® AuraGain™ or Teleflex® LMA Protector™ during insertion and placement into an airway.

**2.2 Secondary:** Rate of successful ventilation and intubation (by utilizing the SGAD as an intubation conduit guided by the Ambu® aScope™ 3 Slim), ease of SGAD insertion (based on a numerical subjective rating scale), anatomical fit of SGAD (i.e. SGAD displacement, bloodstaining), OLP (measured by a portable, handheld manometer), functionality of gastric drainage channel which will be inserted through the appropriate channel of the SGAD, and postoperative complications

**2.3 Exploratory:** Fiberoptic assessment of the glottic view via the SGAD device and signs of airway morbidity

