#### 1. Insertion of the SGAD

The patient will be placed in the sniffing position to optimize the oropharyngeal angle. The SGAD will be lubricated on the posterior surface of the cuff prior to insertion. Timing will begin when the tip of the cuff of the device touches the patient's lips. During insertion, the tip of the cuff will be pressed upwards against the hard palate and the cuff will be flattened against it. Jaw lift technique will be used on all patients. A jaw lift is performed by using the index finger and thumb of the non-dominant hand to lift the chin while the device is passed along the hard palate with the dominant hand. Additional maneuvers performed to optimize positioning or ventilation, such as adjusting head/neck position, additional jaw lift, adjusting depth of insertion, lateral insertion technique, or changing size of the SGAD. For the SGAD to be considered as placed correctly, the teeth of the patient should be between the teeth-marks indicated on the proximal end of the airway tube designed as a bite absorption area. The appearance of the first square end tidal carbon dioxide trace will indicate establishment of effective ventilation, and T1 (watch 1) will be stopped. Once successful placement has been confirmed, the cuff of SGAD will be inflated with air to attain an intra-cuff pressure of 60 cm H2O, measured with a handheld aneroid manometer (pressure gauge). The volume of air will be recorded. The SGAD will be taped to the participant's cheek with adhesive tape.

Unsuccessful appearance of CO2 curve suggests incomplete placement of the SGAD, and the device will be removed completely and another insertion attempt should be performed while the recording of time continues. An insertion attempt is defined as, when the SGAD touches the patient's lips. Only three attempts shall be made for proper device placement. The first two attempts will be made by either attending anesthesiologists or certified registered nurse anesthetists (CRNA) and the final attempt by the attending anesthesiologist. In case of failure of both SGAD and bag-mask ventilation, the airway will be secured according to the discretion of the attending anesthesiologist.

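### Read literally, the adverse event definition excludes any condition that leads to a procedure, so a more severe new injury can lose adverse event status while a milder one keeps it

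*Combined protocol and SAP*

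**What the plan says.** Under Adverse Events Definitions, section 13.0 opens with a wide rule: "An Adverse Event is any undesirable clinical event occurring to the subject during clinical study, whether or not it is considered related" to the product. A list of exclusions follows, and its first item is "Medical or surgical procedures; the condition that leads to the procedure is not an adverse event". A separate item excludes "Pre-existing disease, conditions, or laboratory abnormalities present at the start of the study that do not worsen in frequency or intensity". Another covers situations with no untoward occurrence, with admission for elective surgery as an example. The last is "Expected post-operative course".

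The rest of section 13.0 builds on the AE definition. Under Adverse Events, "adverse events will be categorized at the investigative site into two groups: Serious Adverse Events, and Non-Serious Adverse Events". Each AE is then rated for its relation to the device and, if related, as anticipated or unanticipated. Under Reporting of Adverse Events, AEs go on the Adverse Event Form and the principal investigator reports them to the IRB. A UADE goes to the sponsor within 24 hours.

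**The concern.** The general definition and the first exclusion give opposite answers for one class of event: a condition that is new on study and leads to a procedure. The exclusion also sorts in the wrong direction, because needing a procedure is usually a sign of greater severity.

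The class is not remote in this trial. Under section 8.0 each subject may have up to three device insertion attempts, passage of a gastric tube and up to three intubation attempts through the device. Section 9.0 names oropharyngeal injury among the recognised risks. At stake is whether a coordinator who follows the text would classify, rate and report such an injury as an AE.

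**Working it through.** The plan states no figure on this point, so the check is to follow the text through section 13.0 for two hypothetical injuries. Both are new on study and caused by the device. One needs no procedure; the other leads to one.

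| Rule in section 13.0 | Injury, no procedure | Injury that leads to a procedure |
|---|---|---|
| General AE definition | Met | Met |
| First exclusion, read literally | Does not apply | Applies |
| AE status | AE | Not an AE |
| Serious/non-serious class | Assigned | None, since both classes are subsets of AEs |
| Causality and anticipated/unanticipated ratings | Given | Not required |
| AE Form entry and report to the IRB as an AE | Required | Not required |
| UADE, first part (a device-related AE not matching the product information) | Available | Closed, since it requires an AE |
| UADE, second part (other unanticipated serious device problems) | Available | Available, if unanticipated and serious |
| Recording of serious adverse experiences | If serious | If serious |

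**Does another exclusion narrow the first one?** The pre-existing conditions item already removes stable baseline disease, and the elective surgery example covers the planned admission. Neither limits the first item, which carries no limit of its own. No other text in the protocol gives AE status back to a new condition that leads to a procedure.

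**How far do the backstops reach?**

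- The second part of the UADE definition does not use the term AE, so it survives the exclusion. An unanticipated serious device harm still goes to the sponsor within 24 hours and onto the Adverse Event Form.
- That route needs the problem to be unanticipated. Section 9.0 lists oropharyngeal injury, with bleeding or bloodstaining on placement, as a recognised risk. An injury of that kind may be judged anticipated and so miss the route.
- Under Responsibilities for Reporting Serious Adverse Events, the principal investigator records all serious adverse experiences. The term is not defined, nothing says it overrides the exclusion, and an entry in source documents alone would satisfy the instruction.

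**Size.** The number of affected events cannot be derived from the documents. The effect of losing one can. Section 11.0 gives 25 patients per arm, so one event is 1/25 = 4 percentage points. With exact (Clopper-Pearson) 95% limits:

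- 1/25 observed: 0.1% to 20.4%.
- 0/25 observed: upper limit 1 − 0.025^(1/25) = 13.7%.

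This shows what omitting any single event does to an arm's recorded AE rate. It says nothing about how likely an omission is.

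**The case against.** **The bullet may mean only the planned operation and its indication.** Every subject is scheduled for elective surgery, and exclusion lists often overlap, so the redundancy with the neighbouring items does not prove that new injuries were meant. That is fair, and a deliberate rule to exclude them is not established. But the limit is not written down, and someone applying the words as they stand would omit the event. The sentence needs correcting on either reading.

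**Serious harms are still caught elsewhere.** A reader might infer that such an injury vanishes from the safety record, or that only an AE can reach the 24-hour route. The documents do not support that. The second part of the UADE definition and the serious adverse experience instruction both operate outside the AE term. What stands is narrower: the loss of AE classification, ratings and reporting, mainly for harms judged anticipated.

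**The device comparison is not shown to suffer.** A reader might also infer that the secondary comparison of complications is weakened. Section 2.2 lists "through the appropriate channel of the SGAD, and postoperative complications" among the secondary outcomes, but nothing says these are drawn from AE forms or filtered through the AE exclusions. The case report form in Appendix C is not part of the text reviewed. Section 8.0 foresees a double failure ("In case of failure of both SGAD and bag-mask ventilation, the airway will be secured according to the discretion of the attending anesthesiologist"), which could be read as a condition leading to a procedure. Even so, insertion success is the primary outcome and ventilation success a secondary one, so those failures have their own measures.

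**The last exclusion is a separate matter.** It is tempting to add that "Expected post-operative course" lets investigators leave out airway symptoms. That item refers to recovery after surgery and does not contradict the general definition. Its use to omit device effects is conjecture.

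**Conclusion.** The first exclusion is wrong as written, as a safety-reporting rule. Read literally, it contradicts the general AE definition and removes AE status from a new condition that leads to a procedure, while a milder condition keeps it. The consequence is loss of the seriousness class, the causality and anticipated/unanticipated ratings, the AE Form entry and IRB reporting as an AE. It is only partly offset by the remaining routes. The gap is clearest for device harms judged anticipated.

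The conclusion rests on a literal reading and on the absence of any overriding definition in the protocol. It depends on no assumed event rate. The fault does not affect the primary endpoint, randomisation or sample size, and no effect on the secondary comparison is shown. It is worth correcting promptly but ranks below faults that threaten the trial's main result.

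**What to change.** Reconcile the first exclusion with the AE definition. Suggested wording: *A medical or surgical procedure is not in itself an adverse event. A condition that arises or worsens during the study and leads to a procedure is an adverse event.* The existing item on stable pre-existing disease can stay as it is and will continue to cover the indication for the planned surgery. This point calls for no change to the other exclusions.

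The cost is one revised item in section 13.0 and a matching line in the AE Form instructions. Treatment, endpoints and sample size are untouched, and a few more events may be logged. The change is best made before enrolment or by early amendment, because an event left off the form may be hard to recover later.

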#### Reporting of Adverse Events

All adverse events, whether observed by the Investigator, elicited from or volunteered by the subject, should be documented. Each adverse event will include a brief description of the experience, the date of onset, the date of resolution, the duration and type of experience, the severity, the relationship to investigational product (i.e., drug or device), contributing factors, and any action taken with respect to the study drug/device.

Investigators and research coordinators will be instructed that all AE and corresponding relevant information should be recorded on the Adverse Event Form. In addition, the clinical site will be responsible for notifying Sponsor within 24 hours of any UADE. All relevant information regarding an UADE should be recorded on the Adverse Event Form and reported to Sponsor via Fax within 24 hours of the event. In addition to the event form, copies of adverse device effect related source documents should be forwarded to the Sponsor.

The Principal Investigator is responsible for reporting AEs to the IRB of record in accordance with IRB procedures. The Sponsor is responsible for informing the appropriate regulatory authorities and other Investigators of any UADEs that have occurred.

#### Responsibilities for Reporting Serious Adverse Events

The Principal Investigator will record all serious adverse experiences that occur during the study period in the appropriate source documents and/or AE log as applicable.

### 14.0 Data Monitoring Plan

#### Training of Clinical Site Personnel

The training of clinical site personnel will be the responsibility of the Sponsor. To ensure uniform data collection and protocol compliance, personnel from Sponsor will review the investigational plan, techniques for the identification of eligible subjects, instructions on data collection, methods for soliciting data from alternate sources, and schedules for follow-up, as necessary, with the research coordinator.

#### Data Reporting

All data will be recorded on the site's standard source documentation. The Investigator or designee is responsible for transferring the information to the appropriate Case Report Forms (CRFs) supplied by the Sponsor. The Investigator is responsible for ensuring the forms are accurately completed at the time of, or as soon as possible after, the subject procedure or the availability of test results. The Investigator is required to sign the CRF on the appropriate page(s) to verify that he/she has reviewed the recorded data.

#### Data Review

The Sponsor will review all deidentified CRFs for completeness and clarity upon receipt. Missing or unclear data will be requested as necessary throughout the study. The Sponsor will request further documentation such as physician procedure notes when UADEs and/or malfunctions are observed and reported.

The Sponsor will provide clinical monitoring including comparison of CRFs to source documentation for accuracy and appropriateness, review of/for adverse events, prompt evaluation of UADE, and site compliance. To this end, the Principal Investigator will permit inspection of the study files and subject CRFs by Sponsor representatives and/or responsible government agencies.

Prior to initiation of the study, sites will be trained on the clinical protocol, accepted clinical practices and Federal regulations pertaining to clinical research. Study sites will receive interim monitoring, as needed, and a final visit prior to study closure.

### 15.0 Deviation and Compliance

#### Compliance

It is expected that sites (Investigators, study coordinators, ancillary site personnel, and study subjects) will be compliant with the study protocol. Should it be determined that the site is non-compliant, reasonable efforts will be made to secure compliance.

These efforts/actions shall be documented in writing and maintained within the study administration file at the Sponsor's location.

Should the site continue to remain non-compliant, the study Sponsor may restrict device availability and/or notify the governing IRB. Should efforts to bring the site into compliance fail, the site may be suspended from study participation until the noncompliance is resolved. Federal regulations require the Sponsor to report non-compliances in the study to the appropriate regulatory authorities. Therefore, in the event of an Investigator or site suspension, the governing IRB and other appropriate regulatory authorities shall be notified.

#### Protocol Deviations

Protocol Deviations (PDs) will be documented on a Protocol Deviation Case Report Form. PDs are reportable to the institution's governing IRB and regulatory agencies during the annual reporting process, unless otherwise directed by the individual governing IRB requirements or as the specific circumstance dictates.

Every attempt shall be made to adhere to the study protocol. However, should an Investigator be required to deviate from the protocol to protect the life or physical well-being of a study subject in an emergent circumstance, such notice shall be given to the study Sponsor as soon as possible, but no more than 5 working days from the date the event occurred. With the exception of an emergent circumstance, prior approval from Sponsor and the appropriate regulatory authorities is required for any change in, or deviation from, the study protocol as such changes may affect the soundness of the investigation or the rights, safety, and welfare of study subjects.

